7.1 Allowed Medications and Treatments

All topical drugs (any topical midriatic treatment and any traditional topical therapy for uveitis) will be admitted for the treatment of the signs and symptoms associated with HLA-B27-associated chronic relapsing uveitis.

In the case of relapse with LFM values are > 100 ph/ms despite treatment with topical therapy, or in any case the LFM values result to be > 100 ph/ms, then a systemic therapy is recommended and the subject has to be dropped-out from the study and treated according to the best medical judgement.

7.2 **Prohibited Medications and Treatments**

The following medications are prohibited during the study and the administration will be considered a protocol violation: supplements and nutraceuticals, systemic therapies for uveitis (anti-inflammatory, immunosuppressive, biologicals), hormonal contraceptives, long-term treatment with systemic anti-inflammatory, immunosuppressive or biological drugs for other diseases different from uveitis. Systemic therapies with anti-inflammatory, immunosuppressive drugs are allowed for reasons different from uveitis and in any case for periods not exceeding 15-30 days.

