10.4 Additional Unscheduled Visits in Case of Relapse

Should a relapse occur, an unscheduled visit will be performed including a complete ophthalmic evaluation. The number of cells in the AC will be determined by slit lamp, too.

Topical or systemic treatment will be prescribed to the subject according to the severity of the relapse and according to the best medical judgement.

Two following visits will be scheduled 2 and 6 weeks thereafter. During these visits a complete ophthalmic evaluation will be done.

If the subject is prescribed a systemic treatment for the relapse, he/she will be withdrawn from the study, and treated according to the best medical judgement.

If only topical treatments are prescribed, the subject will be allowed to continue the study. Depending on the onset time of the relapse it could be necessary to delay Visit 2 or Visit 3 around 2 months after the topical treatment conclusion.

Should Visit 2 be delayed, the delay will be recovered by keeping the date of Visit 3 at 12 months.

Should Visit 3 be delayed, the delay will not be recovered.

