### 5.2 Secondary Endpoints

The following secondary endpoints will be examined:

the reduction of the side effects due to HLA-B27-associated uveitis, such as IOP assessed by Goldmann applanation tonometry (APL), cystoid macular edema (central foveal thickness – central 1 mm subfield

Statistical Analysis Plan Version no. 1.0 – 20/07/2020

Protocol Code NORFLO-ORO-16 EudraCT number NA

thickness), assessed by optical coherence tomography (OCT) Spectralis® spectralis, keratopathy, evaluated by fluorescein staining of the cornea (present/absent), and synechiae, assessed by photographic slit lamp (present/absent and if present, involving one or more quadrants; photographs shall be retained to document synechia), after treatment with NORFLO® ORO, when compared to placebo;

the improvement in uveitis-related symptoms (BCVA, symptoms like ocular pain, photophobia, floaters and blurred vision, measured by VAS) after treatment with NORFLO® ORO, when compared to

placebo;

the patients' attitude towards the treatment with NORFLO® ORO, compared to placebo, was captured by means of a questionnaire (Quick Questionnaire) specifically developed for the study on the basis of previous experiences.

These data were reported at visit 1 (baseline), at visit 2 (after 6 months) and at visit 3 (after 12 months). In case of relapse near visit 3, the data collected during the visit 3 will be replaced with the data collected during the first unscheduled visit.

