# 7. SAMPLE SIZE AND STATISTICAL POWER CONSIDERATION

With a statistical power of 80% and a significance level (alpha) of 5% and a common SD of 0.7, 46 patients are needed to observe a difference of 0.6 relapses/patients between the two treatment groups (i.e., 2 relapses/patient in the NORFLO® ORO treatment group vs. 2.6 in the placebo treatment group). To take into account a potential dropout rate of 20% over 12 months, 60 patients were recruited.

A second primary endpoint, i.e. the reduction of mean number of relapses between the year before treatment and the study period, will be examined. No formal sample size estimate was feasible on this endpoint, as it was not tested previously and no reasonable scenario can be drawn.

As the two endpoints will be assessed in a hierarchical order (first, "the mean number and intensity of relapses during the study between treatment groups" and then "the reduction of mean number of relapses between the year before treatment and the study period"), according to the "Points to consider on multiplicity issues in clinical trials", issued

Statistical Analysis Plan Version no. 1.0 – 20/07/2020 Protocol Code NORFLO-ORO-16 EudraCT number NA

by the Committee for Proprietary Medicinal Products (CPMP - 2002), no sample size adjustment for multiplicity was needed.

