# 9.1.4 Methods for Withdrawals and Missing Data

A subject could be discontinued from the study treatment at any time if either the subject, and/or the investigator, and/or Eye Pharma feel that it is not in the subject's best interest to continue the study treatment. The following is a list of possible reasons for study treatment discontinuation:

- Subject withdrawal of consent
- Subject is not compliant with study procedures

Statistical Analysis Plan Version no. 1.0 - 20/07/2020

Protocol Code NORFLO-ORO-16 EudraCT number NA

- Need for the subject to start a systemic anti-inflammatory, immunosuppressive, biologicals therapy for uveitis or for other pathologies
- Adverse event that indicated in the opinion of the investigator that it would be in the best interest of the subject to discontinue study treatment
- Pregnancy
- Protocol violation requiring discontinuation of study treatment
- Missed follow-up
- Eye Pharma requests early study termination.

All subjects who discontinued the study treatment should come back for an early discontinuation visit as soon as possible and then they should be encouraged to complete all remaining scheduled visits and procedures.

All subjects were free to withdraw from participation at any time, for any reason, specified or unspecified, and

Reasonable attempts were made by the investigator to obtain a reason for subject's withdrawals. The reason for the subject's withdrawal from the study was specified in the subject's source documents.

No missing data will be replaced.

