## 11.1 Analysis datasets

All eligible patients who were randomized into the study and received at least one dose of the study product (the Safety Population) will be included in the safety analysis. All eligible patients who were randomized into the study, received at least one dose of the study product and had at least a post-randomization endpoint estimate (the Intention-to-Treat Population) will be included in the efficacy analysis. Primary endpoints will be also analyzed in a modified Intention-to-Treat Population, where the patients with the protocol violations mentioned in the session 10.2 (Protocol Deviations) will be excluded.

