# 11.4.2 Secondary Efficacy Endpoints

The incidence of side effects associated HLA-B27-associated uveitis will be compared between treatment groups. The changes in IOP, in central 1 mm subfield thickness, and the changes in OCT will be compared between treatment

Statistical Analysis Plan Version no. 1.0 – 20/07/2020 Protocol Code NORFLO-ORO-16 EudraCT number NA

groups using ANCOVA, with the baseline level included in the model. The presence of keratopathy and synechiae will be compared between treatment groups using chi-square test.

The changes in BCVA and symptoms (ocular pain, blurred vision, floaters and photophobia), measured by VAS, will be compared between treatment groups using ANCOVA, with the baseline level included in the model.

Each information collected through the Quick questionnaire will be compared between the two treatment groups using chi-square test.

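### Month-12 ANCOVA on the continuous secondary endpoints makes no use of the Visit 2 values of patients who leave; a two-visit repeated-measures model would, with limited gain in bias and power

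*SAP*

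**What the plan says.** - **Method.** SAP 11.4.2 analyses change in IOP, central 1 mm thickness and OCT by baseline-adjusted ANCOVA. BCVA and four symptoms "measured by VAS, will be compared between treatment groups using ANCOVA, with the baseline level included in the model". No analysis visit is named. Table 11.5 assigns the IOP, OCT and BCVA analyses to the ITT population and has no row for VAS.
- **Visits.** SAP 5.2: "These data were reported at visit 1 (baseline), at visit 2 (after 6 months) and at visit 3 (after 12 months").
- **Missing data.** SAP 9.1.4 ends its section on withdrawals with: "No missing data will be replaced". No assumption about the dropout mechanism and no sensitivity analysis is stated.
- **Population.** SAP 11.1: randomised, dosed patients who "had at least a post-randomization endpoint estimate (the Intention-to-Treat Population) will be included in the efficacy analysis".
- **Dropout.** SAP 7: "To take into account a potential dropout rate of 20% over 12 months, 60 patients were recruited". The 20% is used only to size the relapse-count comparison.
- **Withdrawal.** Protocol 10.4: "If the subject is prescribed a systemic treatment for the relapse, he/she will be withdrawn from the study". Protocol 7.1 adds a flare trigger: "in any case the LFM values result to be > 100 ph/ms, then a systemic therapy is recommended", and the patient leaves the study.
- **Other values.** Protocol 10.5 repeats the Visit 3 assessments at early withdrawal. For a relapse close to Visit 3, SAP 5.2 says "the data collected during the visit 3 will be replaced with the data collected during the first unscheduled visit". How close is not defined.

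**The concern.** A patient with a Visit 2 value but no Visit 3 value meets the ITT definition, yet cannot enter a month-12 ANCOVA when nothing is filled in. The analysis labelled ITT then becomes a completers' comparison. Naming Visit 3 as the analysis visit would not change that.

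The loss is unlikely to be random, because the protocol withdraws patients for worsening disease. If patients doing badly leave one arm more often than the other, the completers are no longer comparable, and a spurious difference can appear or a real one shrink. Some precision is lost as well, because measurements already taken on those patients at 6 months are not brought to bear on month 12.

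**Working it through.** **The plan's own figure.** For a difference of 0.6, SD 0.7, 5% alpha (taken as two-sided) and 80% power, the normal approximation gives n = 2 × (1.960 + 0.842)² × (0.7/0.6)² = 21.4, so 22 per arm (44). The exact t calculation gives 79.3% power at 22 per arm and 81.1% at 23, so 46 reproduces. 46/0.80 = 57.5, so 58; the plan takes 60. With 30 per arm and 20% dropout, 24 per arm reach Visit 3. No secondary endpoint has a stated effect, SD or power, so everything below rests on assumed values.

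**Power.** Let n₃ be the number per arm with Visit 3, n₂ the number with Visit 2, and r the correlation of Visit 2 with Visit 3 given baseline. Under monotone dropout, the repeated-measures Visit 3 contrast has effective size

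n_eff = 1 / [(1 − r²)/n₃ + r²/n₂].

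Take the standardised effect that gives 80% power at 24 per arm: √(2/24) × 2.802 = 0.81 SD. Example with n₂ = 27 (half the dropouts seen at Visit 2) and r = 0.5: 0.75/24 + 0.25/27 = 0.0405, so n_eff = 24.7 and power is 81.1%.

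| r | all leave before Visit 2 (n₂ = 24) | half seen at Visit 2 (n₂ = 27) | all seen at Visit 2 (n₂ = 30) |
|---|---|---|---|
| 0.3 | 80.0% | 80.4% | 80.7% |
| 0.5 | 80.0% | 81.1% | 82.0% |
| 0.7 | 80.0% | 82.2% | 83.9% |
| 0.9 | 80.0% | 83.6% | 86.4% |

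With no dropout, power would be 87.9%. The gain is therefore 0 to 6.4 points of the 7.9 lost, and 0.4 to 3.6 points if half of the dropouts were seen at Visit 2.

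**Simulation with a true effect** (30 per arm, 0.7 SD, 20% dropout all after Visit 2, correlation 0.6; ANCOVA against the two-visit likelihood estimate):
- random dropout: power 77.1% v 78.0%;
- moderate dependence on Visit 2: 74.2% v 77.4%, mean estimate 0.673 v 0.695;
- strong dependence on Visit 2: 71.7% v 77.3%, mean estimate 0.641 v 0.693.

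A second simulation with these same inputs gave 78% v 82% and 0.65 v 0.70 under strong dependence, about no gain under random dropout, and 0.57 v 0.58 when dropout followed unobserved status. Absolute power differs between the two, so the differences are what to read: 5.6 and about 4 points under strong dependence.

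**Simulation of bias with a true effect of zero** (60 patients, 4000 trials, all three visits with SD 1, higher is worse). In the first two rows, active dropout is a flat 10% and placebo dropout has log-odds −1.3 + 1.5 × the driving value, about 28%. In the third row, dropout falls in both intervals, about 27% on placebo and 10% on active. Overall dropout is 18% to 19%. Bias in SD units at visit correlation 0.5 / 0.7:

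| Dropout driven by | ANCOVA | Repeated measures |
|---|---|---|
| observed Visit 2 value | 0.082 / 0.066 | 0.002 / −0.001 |
| unobserved status after Visit 2 | 0.236 / 0.165 | 0.212 / 0.139 |
| unobserved status in both intervals | 0.182 / 0.125 | 0.170 / 0.113 |

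Share of bias remaining in the last two rows: 0.212/0.236 = 90%, 0.139/0.165 = 84%, 0.170/0.182 = 93%, 0.113/0.125 = 90%.

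**The case against.** The strongest objection is that the mechanism which makes dropout informative here is not the one the model corrects. Withdrawal follows a relapse needing systemic treatment, or a high flare reading. Both can occur between scheduled visits, outside any model of Visits 2 and 3. Protocol 10.4 also lets Visit 2 be delayed until about two months after topical treatment ends, when the eye may be quiet and the value says little about the relapse. This stands. A reader might infer that a repeated-measures model removes dropout bias; the withdrawal rules and the bias figures do not support that.

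Further points that stand:
- The SAP names no visit, so Visit 2 may be tested on its own. That its data are thrown away altogether cannot be read from the text. What can be said is that they do not inform a month-12 ANCOVA.
- Protocol 11.1 and SAP 9.1.4 encourage patients who stop treatment to complete their visits, so fewer Visit 3 values may be missing than 20% implies. Protocol 11.2 replaces patients who start systemic therapy, but that does not supply the missing month-12 value of the patient who left.
- Both eyes are examined (Protocol 9.2), so a model with one value per patient per visit needs an eye rule. SAP 11 and 13 also plan non-parametric tests for non-normal variables, which the model does not replace.

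It can also be said that baseline-adjusted ANCOVA is an accepted choice for unpowered secondary endpoints in an exploratory trial. That limits the importance of the point but does not answer it. The ITT label still does not match what a month-12 ANCOVA would use, and in no dropout scenario tested was the two-visit model more biased.

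**Conclusion.** The concern holds in limited form. The ANCOVA with nothing filled in leaves ITT patients without a Visit 3 value out of the month-12 comparison, and a two-visit model puts their data to use.

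- **Bias.** The model removes bias from dropout that depends on baseline and Visit 2 values (0.07 to 0.08 SD in the example). Where dropout follows unobserved status, 84% to 93% of the bias remains. These sizes depend on the assumed difference in dropout between arms.
- **Power.** The gain is about 0 to 6 points at 20% dropout, under assumed effects and correlations. The upper end needs every dropout to have been seen at Visit 2 and r near 0.9, or dropout strongly dependent on the Visit 2 value. Patients who leave before Visit 2 contribute nothing. The documents do not give the timing of dropout.

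A reader might go further and conclude that the lost power is restored, or that the change is free. Neither follows: no secondary endpoint has a documented power to restore, and the model needs a stated assumption and several data rules that the SAP lacks. The point concerns the secondary endpoints only.

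**What to change.** In SAP 11.4.2 and table 11.5:

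1. Replace the ANCOVA for IOP, central 1 mm thickness, BCVA and each VAS symptom by one repeated-measures model per endpoint over Visits 2 and 3. Include treatment, visit, treatment-by-visit, baseline, baseline-by-visit and site, with an unstructured 2×2 covariance and Kenward-Roger degrees of freedom. Name the Visit 3 treatment contrast as the result. The site term also carries out the adjustment promised in SAP 9.2.
2. Add the missing VAS row to table 11.5. Keep the planned non-parametric analysis as a supplement.
3. State the missing-at-random assumption in SAP 9.1.4, and add a delta-adjusted or reference-based sensitivity analysis for patients withdrawn because of a relapse.
4. State one rule for which eye's value is analysed.
5. Keep early-withdrawal values out of the month-12 position. Settle how the SAP 5.2 replacement of Visit 3 data by the relapse visit enters the model; as written, it puts values from an acute relapse into the 12-month endpoint.
6. Reconcile Protocol 10.4, which takes patients out of the study, with Protocol 11.1 and SAP 9.1.4, which encourage remaining visits after treatment stops.

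The cost is modest SAP wording, some extra analysis in SAS and an explicit missing-at-random assumption. No new data are needed. The change should be made before database lock and unblinding.

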10 EVALUATIONS BY VISIT

10.1 Visit 1 (t₀)

- 1. Review the study with the subject (subject's legal representative) and obtain written informed consent
- 2. Assign a unique screening number to the subject
- 3. Record subject's demographics data
- 4. Record subject's medical history, including a history of uveitis, diagnosis date and prior uveitis treatments and the number of relapses during the previous year
- 5. Record subject's concomitant medications
- 6. Perform a physical examination of the subject
- 7. Vital signs collection
- 8. Urine dipstick specific pregnancy test
- 9. Perform a rheumatologic evaluation of the subject
- 10. Perform subject's ophthalmic evaluation (BCVA, Slip lamp, OCT Spectralis[®], LFM, Goldman tonometry).
- 11. Evaluation of uveitis symptoms by VAS (ocular pain, blurry vision, floaters, photophobia)
- 12. Evaluation of the patient's attitude towards the study treatment, through the Quick Questionnaire
- 13. Evaluate inclusion/exclusion criteria adherence
- 14. Randomize subject and dispense study product
- 15. Initiate subject diary.

After about 3 months of treatment the study staff will contact the patient by phone to verify that the study product is correctly taken.

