## 11.5 Summary of Efficacy Analyses

| Endpoint   | Analysis  | Populations |
|--|---|-------------|
| The mean number and intensity of relapses
(primary endpoint)                | Student's t-test, ANOVA, generalized linear mixed model | ITT         |
| The reduction of mean number of relapses (primary endpoint)                    | Student's t-test, ANOVA                                 | ITT         |
| The difference of the level of cell damage and inflammation (primary endpoint) | ANCOVA  | ITT         |
| The changes in IOP (secondary endpoint)  | ANCOVA  | ITT         |
| The changes in OCT (secondary endpoint)  | ANCOVA  | ITT         |
| The changes in BCVA (secondary endpoint)                                       | ANCOVA  | ITT         |
| The presence of keratopathy (secondary endpoint)                               | Chi-square test   | JTT         |
| The presence of synechiae (secondary endpoint)                                 | Chi-square test   | ITT         |
| Information collected through the Quick questionnaire (secondary endpoint)     | Chi-square test   | ITT         |

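### The Quick Questionnaire is compared item by item with a plain chi-square that, as written, uses neither the Visit 1 answer, nor site, nor any ordering of the answers; this can cost power on a secondary endpoint

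*SAP*

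**What the plan says.** Protocol 10.1 lists, among the Visit 1 procedures, "Evaluation of the patient's attitude towards the study treatment, through the Quick Questionnaire". It is step 12; randomization and dispensing are step 14. Protocol 10.2, 10.3 and Appendix 1 repeat the questionnaire at Visits 2 and 3. SAP 5.2 confirms the three time points, and SAP 9.1.1 defines the Visit 1 values as baseline.

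The analysis is one sentence in SAP 11.4.2: "Each information collected through the Quick questionnaire will be compared between the two treatment groups", by chi-square. Protocol 14.4 and the summary table in SAP 11.5 give the same test. None of them names a baseline term, a change score, an ordinal test or an analysis visit.

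In the same SAP section, the changes in IOP, OCT, BCVA and VAS symptoms are compared between treatment "groups using ANCOVA, with the baseline level included in the model". SAP 9.2 states, as a general rule, that the analysis is adjusted for clinical site.

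On the instrument itself, SAP 5.2 says only that it was "specifically developed for the study on the basis of previous experiences". The items, their response options and any ordering of those options are not given.

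**The concern.** The trial collects a pre-randomization answer to each item, and the planned test, taken literally, does not use it. A Pearson chi-square on an arm-by-answer table has no place for a baseline covariate or a site term. It also treats graded answers as unordered labels. An effect that moves patients up or down a scale is then spread over several degrees of freedom instead of being tested on one.

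What is at stake is precision on one secondary endpoint, patients' attitude to treatment, in a trial of 23 to 30 patients per arm. Chance imbalance in the Visit 1 answers stays as noise in the later comparison. SAP 9.2 and SAP 11.4.2 also do not fit together for this endpoint, whatever the response format.

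**Working it through.** **Patients per arm.** The only sample size in the plan is for the primary endpoint (Protocol 14.7): difference 0.6, SD 0.7, alpha 5%, power 80%. The normal formula gives 2 × (1.96 + 0.84)² × 0.7² / 0.6² ≈ 21.4, so 22 per arm. The t-based version needs 22.4, so 23 per arm, or 46 in total (power 81.1%), as stated. Allowing for dropout, 46 / 0.8 = 57.5, so 58 against the 60 recruited. The range is therefore 23 (evaluable) to 30 (randomized) per arm. No power is stated for the questionnaire.

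**Assumed model, graded items.** The latent answer at follow-up is ρ × (latent baseline) + √(1 − ρ²) × (noise) + 0.75 × (arm). Baseline and follow-up are cut into 3 or 5 equally likely levels. The shift of 0.75 SD, the number of levels and ρ are all assumptions. There were 3000 simulated trials per power setting, two-sided 5%.

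**Tests.** (a) Pearson chi-square on the arm × level table; (b) Wilcoxon test; (c) rank ANCOVA, in which rank(follow-up) is regressed on arm and rank(Visit 1 answer) and the arm term is tested.

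Power in %, as (a) / (b) / (c), without site:

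| ρ | 3 levels, 23/arm | 3 levels, 30/arm | 5 levels, 23/arm | 5 levels, 30/arm |
|---|---|---|---|---|
| 0 | 47.8 / 57.9 / 57.6 | 60.2 / 71.1 / 70.5 | 38.4 / 61.9 / 62.6 | 53.1 / 75.4 / 75.1 |
| 0.3 | 47.9 / 58.5 / 59.8 | 60.2 / 69.9 / 72.6 | 40.9 / 63.5 / 66.9 | 52.5 / 75.0 / 78.2 |
| 0.5 | 47.5 / 58.7 / 65.5 | 59.3 / 69.8 / 76.8 | 40.2 / 63.8 / 73.8 | 50.8 / 74.5 / 83.2 |
| 0.7 | 48.7 / 59.1 / 74.9 | 60.8 / 70.0 / 85.5 | 40.2 / 63.5 / 84.3 | 52.5 / 76.0 / 92.7 |

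The two sources of loss separate. At 30 per arm, five levels and ρ = 0.5, ordering accounts for 74.5 − 50.8 = 23.7 points and baseline for 83.2 − 74.5 = 8.7. With three levels the figures are 69.8 − 59.3 = 10.5 and 76.8 − 69.8 = 7.0. At ρ = 0 the baseline term adds essentially nothing and the whole gain is from ordering.

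**Yes/no items.** True proportions 50% and 80%, chi-square against a Mantel-Haenszel test stratified by the Visit 1 answer. At 30 per arm the powers are 69.5 and 69.2 (ρ = 0), 68.6 and 70.1 (0.3), 69.2 and 73.6 (0.5), 69.2 and 79.2 (0.7).

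**Type I error.** With no effect, every test above rejected in about 4-6% of trials.

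**Adding site.** With rank ANCOVA on baseline and four sites (the number in the Protocol Synopsis) and the 0.75 SD shift at 23 to 30 per arm, type I error stayed near 5%. Change in power against the plain chi-square:

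| Item type | ρ 0-0.3 | ρ 0.5-0.7 |
|---|---|---|
| 3 levels | about +7 to +11 | about +15 to +25 |
| 5 levels | about +17 to +22 | about +28 to +41 |

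For yes/no items the change ran from about −4 points at ρ = 0 to about +6 to +8 at ρ = 0.7.

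**Proportional odds.** For a five-level item with no effect, a likelihood-ratio test from a proportional-odds model with baseline and four sites rejected in about 6.5-7% of 800 trials per setting (standard error about 0.9), a mild excess.

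**Sparse tables.** With 46 patients and five levels, the average expected count is 46 / 10 = 4.6 per cell. SAP 11.4.2 names no small-sample alternative for this comparison.

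**The case against.** The strongest reply is that the instrument is not shown. If the items are yes/no or unordered, the ordering argument disappears. The construct is attitude to a product the patient has not yet taken, so the Visit 1 answer may predict little; at ρ near 0 the baseline term gains nothing. If the true shift is small, the choice of test matters little: at 0.3 SD and ρ of 0-0.5, every method, adjusted or not, has only about 8-22% power. All of this stands, and it is why the size is given as a range.

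Chi-square is also not useless. It is valid under randomization and needs no scoring or model assumption. A reader might infer that the plan loses power for no benefit whatever the items look like. The documents do not support that: for yes/no items with weak baseline correlation, the adjusted analysis with site can be a few points worse.

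Nor do the documents prove that the Visit 1 answer can never enter. A chi-square can be run on a before/after category, as SAP 11.4.1 does for relapse responders, and a site-stratified Mantel-Haenszel version can carry site. But SAP 11.4.2 specifies neither, so as written both are absent.

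Finally, the contrast with BCVA and VAS is weaker than it looks, because those are scale measurements. The SAP also uses chi-square for keratopathy and synechiae, which have slit-lamp examinations at baseline. That makes the plan consistent for categorical data. It does not supply a reason to set a collected baseline aside.

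**Conclusion.** The point holds as a conditional loss of efficiency on one secondary endpoint with no stated power. The gaps in the text are certain: no baseline term, no site term, no ordinal test and no analysis visit for the questionnaire. The size is not certain. It rests on an assumed 0.75 SD shift, assumed response formats and assumed baseline correlations, with 23 to 30 patients per arm. Under those assumptions the loss is material for graded items even when the baseline answer predicts little, and small or absent for yes/no items.

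A reader might go further and infer that the questionnaire comparison is biased, or that the trial's main result is in doubt. Neither follows. Baseline imbalance after randomization is chance noise, the chi-square keeps its type I error, and no primary conclusion depends on this endpoint. This is an improvement worth making, not a defect that invalidates an analysis.

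**What to change.** Amend SAP 11.4.2 and 11.5 before unblinding, which SAP 4.3 places after database lock:

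- State the items, their response options and the analysis visits (Visits 2 and 3).
- For graded items, replace chi-square with rank ANCOVA, or a site-stratified row-mean-score test, adjusting for the Visit 1 answer to the same item and for site. Do not rely on a likelihood-ratio proportional-odds test at this sample size without first checking its type I error.
- For yes/no items with a meaningful pre-dose answer, use logistic regression or a Mantel-Haenszel test with the Visit 1 answer and site.
- For unordered items, or items with no meaningful pre-dose answer, keep chi-square in site-stratified form.

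The cost is SAP wording only, with no new data. The downside is little or no gain, or a loss of a few points, if the items are yes/no and the Visit 1 answers predict little.
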